All paper and electronic data collection forms, videos from the balance sessions, and output of Mobility Lab system and Actiwatch will be coded and not use the subject's name or other PHI in the subject ID. All subject-identifying information will be uploaded immediately after test session (Mobility Lab system) or when returned after wearing sensors/Actiwatch at home, to be stored and managed securely on our laboratory database, located on an OHSU-approved secure server. Subject confidentiality will be maintained in accordance with HIPAA regulations. Only individuals who are specifically authorized to view PHI by the investigator will have access to information that could be used to identify the subjects. Data will be stored at minimum for five years after the final publication related this project, and at maximum, indefinitely, if subjects also sign our Balance Disorders Laboratory Data Repository consent form (eIRB# 7997).

b. Sharing of Results with Subjects

There is no plan to share results with the subjects, aside from availability of final published manuscripts.

c. Data and Specimen Banking

If subjects also sign our Balance Disorders Laboratory Data Repository consent form (eIRB# 7997), then their data will be stored indefinitely in the repository (located on secure OHSU server).

8. Data Analysis

Aim I: We will collect a number of metrics related to activity level (such as, percentage of the day spent active, number of steps per day/hour, number of turns per day/hour). In addition, we will collect metrics related to the quality of gait and balance (such as mean and variability of: stride length, percentage of time spent in double support, foot strike angle, turn angle, turn velocity). We will undertake analyses to determine which of our metrics are significantly different between Week 1 (before GOCOVRI) and Week 6 (after GOCOVRI) groups with paired t-tests (if data appear normally distributed) or nonparametric Wilcoxon signed-rank test (data not normally distributed). We expect to see the significant change in some of our metrics (e.g., number of turns per day, percentage of the day active, stride time variability) due to improvement in LID symptoms. This result would indicate that GOCOVRI helps increase the overall activity level in addition to improving LID symptoms.

Aim II: We will also separately examine the first hour of sensor data recording each day to see the overnight effect of GOCOVRI™ on activity and balance/gait. We will undertake analyses to determine which of our metrics are significantly different during the first hour of the day between Week 1 (before GOCOVRI) and Week 6 (after GOCOVRI) groups with paired t-tests (if data appear normally distributed) or nonparametric Wilcoxon signed-rank (data not normally distributed). We expect to see a significant change in metrics related to activity level especially during the first hour of the day before the levodopa intake as some subject with PD may have difficulty in initiating walking during the first hour of the day. This result would indicate that GOCOVRI is also helping patients to overcome the difficulty in initially walking during the first hour of the day before the levodopa intake.

Finally, we will explore the opportunity to identify which metrics of gait and balance best relate to LID and the medication fluctuations throughout the day to further understand how LID affects mobility.

9. Privacy, Confidentiality, and Data Security

Subject privacy. Recruitment will take place over the telephone with the researcher in a private office. Consenting will occur during a remote meeting prior to the first study visit with only study team member(s) present. Likewise, during the remote visits only study team members will be present.

Data privacy. Upon consent, a subject ID# will be assigned for a subject and all data files will only have this number on it – the ID number will not contain any of the 18 HIPAA identifiers. The file containing the link between subject name and ID# will be maintained on an encrypted lab computer, in an electronic-access office, and file will only be accessible by study team members who need it. After test session, electronic data will be uploaded to our laboratory database and in a web-accessible REDCap database that is located on a secure OHSU server. Any paper files will be kept in electronic-access only lab offices.

10. Provisions to Monitor the Data to Ensure the Safety of Subjects

Unanticipated events (UPs), protocol deviations/non-compliance, and adverse event (AE) data will be collected from the time the consent form is signed until the participant completes their study participation. AEs may be volunteered spontaneously by the participant, during telephone follow-ups, or be discovered as a result of general questioning during study visits. All study team members are responsible for recording UP, AE, and SAE information.

Unanticipated events (UPs): A unanticipated event is an unexpected (in frequency or severity) occurrence that is related or possibly related to the research project and places the subject at greater risk of harm than was previously known or recognized. All study team members are responsible for monitoring for UPs and reporting to the PI in a timely fashion (3 business days). The investigator will evaluate all UPs and take appropriate action as a result. UPs that place the subject at greater risk of harm will be reported to the OHSU eIRB within 5 business days of occurrence.

Protocol Deviations and non-compliance (PVs). All study team members are responsible for conducting the study according to the protocol and periodic evaluations will be conducted by the investigator to ensure protocol adherence. Major protocol deviations/non-compliance will be reported to the OHSU eIRB within 5 business days. All other protocol deviations/non-compliance will be reported in aggregate at continuing review/check-in. Modifications to the protocol will be approved by the institutional review board prior to implementation by the study staff.

Adverse Events: An adverse event (AE) is any untoward medical occurrence in a participant occurs during a clinical trial which does not necessarily have a causal relationship with the treatment. An AE is any unfavorable and unintended sign, symptom, or disease temporally associated with the administration of treatment, whether or not related to the treatment (study drug or placebo). An AE could be absent at baseline, or if present, appears to worsen during the study treatment. Mild/moderate AEs that are not serious will be reported in aggregate at time of continuing review/check-in.

Serious Adverse Events (SAE). A serious adverse event is (SAE) defined as any untoward medical occurrence that at any dose results in one of the following outcomes:

- Death

- A life-threatening adverse drug experience
- Results in inpatient hospitalization or prolongation of existing hospitalization
- A persistent or significant disability/incapacity
- A congenital anomaly/birth defect

Important medical events that may not result in death, be life threatening, or require hospitalization may be considered a serious adverse drug event when, based upon appropriate medical judgment, they may jeopardize the subject and may require medical or surgical intervention to prevent one of the outcomes listed in this definition.

The PI will real-time monitor AEs/SAEs with SAEs reporting to the OHSU IRB within 5 days of the study staff learning of the event. The AE form will be used to record events.

All events will be evaluated for:

(1). Date(s) of Occurrence.

Start Date – “Start Date” is the day the AE began. If a previously recorded AE worsens, a new record should be created with a new start date. There should be no AE start date prior to the date of the informed consent. Any AE that started prior to the informed consent date belongs instead in the medical history. If an item recorded on the medical history worsens during the study, the date of the worsening is entered as an AE with the start date as the date the condition worsened. The start date is recorded to determine an AE’s temporal relationship to the study intervention. For example, if an aggregate listing of AEs indicate a high number of reported fainting incidents in a study of treatment for epilepsy, the study statistician is likely to investigate the relationship between the reported events and the administration of the study treatment.

End Date – “End Date” is the day the AE resolved or the day the AE worsened. If an AE worsens, record an end date and create a new AE record with a new start date and severity.

(2). Temporality. new event or existing event

(3). Expected. anticipated or unanticipated

(4). Severity. Mild, Moderate, Severe, Life-Threatening/disabling, Death

Severity – The severity of an event is the investigator’s assessment of the intensity of the AE. Severe events interrupt the participant’s/subject’s normal daily activities and generally require systemic drug therapy or other treatment; they are usually incapacitating. Consequently, a change in severity may constitute a new reportable AE. Severity is not synonymous with seriousness (see full definition of SAE, above). A severe rash is not likely to be an SAE. Likewise, a severe headache is not necessarily an SAE. However, mild chest pain may result in a day’s hospitalization and thus is an SAE.

(5). Relatedness to study. Unrelated, Unlikely, Probable, Possible, Definite.

Relatedness – The relationship to the study intervention is the investigator’s assessment of the degree of “relatedness” of the AE to the study intervention. Before beginning a study, definitions for each of the relatedness responses should be supplied.

(6). Action taken.

With study intervention– None, study intervention interrupted, study intervention discontinued, study intervention modified.

Other actions taken– None, Non-Study Treatment Required. If treatment was required, then the corresponding treatment needs to be recorded on the Prior and Concomitant Medications CRF.

(7). Outcome. Not Recovered/Not Resolved, Recovered/Resolved, Recovered/Resolved with sequelae, . Recovering/resolving, Fatal, (f) Unknown.

The outcome of an AE may not be captured at the visit during which it was first reported, but must be captured to provide a complete picture of the event. Entering the outcome of an AE may be deferred until the AE is resolved, or the participant/subject completes the study. For AEs that have not resolved at the time of a study visit, the outcome should be marked as “unresolved” on the AE case report form.

(8). Serious Adverse Event (SAE): Yes, No

This question should only be answered YES if the AE meets at least one of the criteria listed in the General Instructions under the Serious Adverse Event heading. If an AE is serious, this provides a trigger that additional information must be provided by the investigator. The investigator then completes a serious AE form and follows reporting procedures.

Interim safety review will only take place if 3 or more Serious Adverse Events occur within six months. Otherwise, there are no other interim safety reviews planned and there are no predetermined stopping rules.

If the PI has any concern that adverse event is related to the study drug she will have a discuss with patient and study team and if event is of a significant or serious nature the study drug will be stopped. If further medical evaluation or care if needed the PI will direct this.

Conflict of Interest: A co-investigator ([name] PhD) has a conflict of interest with this study. She has a financial interest in the APDM company that makes the Opal sensors utilized in this protocol. The principle investigator will ensure that [name] is not involved in determining subject eligibility, consenting or enrolling subjects, evaluating or reporting UPs, AEs, SAEs, and protocol deviations or non-compliance. [name] will not be involved in the statistical analysis of this project. The nature of this financial interest and the design of the study will be reviewed by committees at OHSU. They will put in place a plan to help ensure that this research study is not affected by the financial interest. We will disclose this conflict of interest to the participants in the informed consent form.

11. Risks and Benefits

a. Risks to Subjects

Falls. Subjects who have neurological condition that can affect gait and balance (e.g., Parkinson’s disease) may be at a risk of falling. During the remote test sessions, the study staff will advise that the subject have a family member available to assist them, and the balance assessments will consist of only a few standing tests.

Loss of Confidentiality. There is a minimal risk of the loss of confidentiality, however this risk will be minimized by the measures mentioned in section 9, above, to restrict access to data and keep it stored safely.

Study Drug (GOCOVRI®).

GOCOVRI may interact with other anticholinergic drugs, carbonic anhydrase inhibitors, sodium bicarbonate, alcohol, and “live” vaccines. GOCOVRI is not recommended for use during pregnancy; it may harm a fetus. GOCOVRI passes into breast milk but its effect on nursing infants is unknown. GOCOVRI may alter breast milk production or excretion.

We will be using GOCOVRI for its FDA approved indication of dyskinesias in Parkinson’s disease. With a gradual withdraw of the drug there should be minimal risk for significant side effects. If after the withdraw dyskinesias are bothersome to the patient and they wish to restart GOCOVRI we will reach out to their provider and share their interest in wanting to remain on the medication. It will be explained to patients that they will only be guaranteed to receive GOCOVRI during the course of the study and future use will be at their and their provider’s discretion with cost as determined by their individual insurance and pharmacy providers. Immediate release amantadine is the same active compound in a different formulation and is a very commonly used, very affordable, and usually readily accessible to most patients. Dyskinesias are generally treated for patient comfort and lack of treatment is not felt to be of short-term, serious medical risk as long as medications are not abruptly stopped.

Common side effects: The most commonly observed adverse reactions occurring at a frequency of >10% and greater than placebo in prior studies were hallucinations, dizziness, dry mouth, peripheral edema (swelling of the extremities), constipation, falls, increase in impulse control/compulsive behaviors, and dizziness on standing (orthostatic hypotension).

Less common side effects: Anxiety, (7%) insomnia (10%), abnormal dreams (5%), confusion (5%), headache (6%), nausea (5%), vomiting (3%), gait disturbance(5%), bruising (6%), urinary tract infection, changes in skin pigmentation (6%), decrease appetite (6%), blurred vision(4%), cataracts (3%), dry eyes (3%), joint swelling (3%), muscle spasms (3%), noncancerous enlargement of the prostate gland (benign prostatic hyperplasia; 6%), dry nose (5%), and cough (3%)

Rare but serious side effects: somnolence and fatigue (4%; daytime sleepiness or episodes of falling asleep during activities that require full attention), suicidality (≤2%) and depression (6%), apathy (2 %), confusion (3%).

Neuroleptic Malignant Syndrome. Rapid withdrawal of GOCOVRI® could result in a symptom complex called neuroleptic malignant syndrome. This syndrome is a life-threatening neurological disorder. Symptoms include: high fever, sweating, unstable blood pressure, stupor, muscular rigidity, and autonomic dysfunction. Adverse event phone calls post-titration down will occur each week by a medical professional.

Alcohol. Alcohol consumption may increase the potential for central nervous system effects such as dizziness, confusion, lightheadedness, and orthostatic hypotension. The participant will be warned that alcohol consumption may increase the potential for central nervous system effects such as dizziness, confusion, lightheadedness, or a drop in blood pressure when standing. Participants will

be advised to limit alcohol use to a minimum and any participant consuming more than 2 drinks a day will be excluded from participation.

Pregnancy. Nursing an infant and pregnant women will be excluded from the study. This study may involve risks to an embryo, fetus, or nursing infant that are currently unknown. If you are sexually active and could become pregnant, you and your male partner(s) must use effective birth control or not have sex. If a participant becomes pregnant during the research study, they must tell the investigator and their PCP immediately. The study drug will be stopped immediately and subject will be removed from the study.

The drug in this study may damage sperm or be present in seminal fluid. Men should not father a child or donate sperm while in this study. If one is a sexually active male and could cause a pregnancy, one must be sure that effective birth control is used or not have sex. The study drug may involve risks to an embryo or fetus that are currently unknown. If a sexual partner becomes pregnant during the research study, they must tell the investigator and have their partner tell her PCP immediately.

b. Potential Benefits to Subjects

There is no expected direct benefit to subjects.

12. Drugs or Devices (delete if not applicable)

This is an investigator-initiated study funded through a grant from the drug manufacturer. The drug being studied is being studied for its FDA approved use for "The treatment of dyskinesias in patients with Parkinson's disease receiving levodopa-based therapy". We will follow all applicable Research Pharmacy policies and procedures and provide the research pharmacy with a manual for the study drug.

Also see the [ICH-GCP guidance](#) for a summary of investigator and sponsor responsibilities in clinical trials.

References:

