1. Protocol Title

Effect of GOCOVRI on Quantity and Quality of Gait in Parkinson's disease

2. Objectives

Aim I: Investigate the effect of GOCOVRI™ on activity levels in people with Parkinson's disease (PD) and Levodopa induced dyskinesia (LID)

Hypothesis I: We hypothesize that GOCOVRI™ will result in an increase of daily activity due to improvement in LID symptoms.

Primary outcome measures: Total number of steps and turns per day

Aim II: Investigate the effect of GOCOVRI™ on comprehensive measures of gait and balance quality in people with PD with LID

Hypothesis II: We hypothesize GOCOVRI™ may improve discrete characteristics of gait and balance that is evident even within the first hour of the day walking.

3. Background

Levodopa induced dyskinesia (LID) is a symptom of Parkinson's disease for which there are limited treatment options. LID leads to reduced quality of life, increased caregiver burden and an increased risk of falls (Rascol et al., 2015, Chapuis et al., 2005). GOCOVRI™ is an extended release capsule prescription medication shown to reduce LID in people with PD (Pahwa et al., 2017, Pahwa et al., 2018). However, a number of studies have identified an increase in falls in those on the active medication study arm but not the placebo arm (13% increase in active and 7% in placebo) (Pahwa et al., 2017). In order to understand this increase in falls, comprehensive measurements of quantity of activity (gait measured in the home environment) and quality of activity (comprehensive gait characteristics that may increase risk of falls) need to be assessed in participants taking GOCOVRI™. In addition, the evidence for the effect of GOCOVRI™ on gait and balance in PD is limited (Smulders et al., 2016).

4. Study Design

This is an open label study in which the participants with PD will know they are taking medication and the experimenters will know which study visits and 7 days of monitoring are baseline, prior to taking GOCOVRI, and which study visits and 7 days of monitoring are after taking maximum dose of GOCOVRI after 5 weeks. Subjects will be given Amantadine extended release for purposes of this study.

5. Study Population

a. Number of Subjects

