A total of 12 people with PD and LID will be recruited to the study. Primarily, participants are to be recruited from the OHSU Movement Disorders Clinic by [name]. In addition to this, we have a laboratory database of PD volunteers for which we have information on LID from previous studies and for which [name] will assist in reviewing. Finally, neurologists in the OHSU Movement Disorders Clinics will be alerted to the study by [name] so they can refer suitable participants.

b. Inclusion and Exclusion Criteria

Subjects will be included in the study if they have:

- 1) a confirmed diagnosis of idiopathic Parkinson's disease by a movement disorders specialist and in accordance with the UK Brain Bank Criteria, 2) Hoehn & Yahr scores of II-IV, 3) aged between 50-85 years

old, 4) subjective report of experiencing at least 1h/day (two, half-hour periods) of ON time with troublesome LID, 5) ambulation with or without aids (e.g., walker or cane), 6) ≥ 30 days of a stable regimen of anti-Parkinson medications that includes a levodopa dose administered ≥ 3 times daily 7) a stable dose of levodopa throughout the study and 8) no amantadine for a minimum of 30 days prior to enrollment in to the study.

Subjects will be excluded from the study if they have: 1) other medical conditions which significantly affect mobility e.g., neurological/musculoskeletal disorders, 2) orthostatic hypotension at screening (defined as a drop of ≥ 20 mm HG systolic and ≥ 10 mm HG diastolic at 2 or 5 minutes of quiet standing after 5 minutes of supine rest), 3) a major psychotic disorder, 4) contraindication to GOCOVRI™ at time of screening, especially renal impairment estimated by glomerular filtration rate (eGFR) < 50 ml/min/1.73 m²) as impaired renal function can increase the chances of adverse reactions to the study drug, 5) mild to severe cognitive impairment as measured by Montreal Cognitive Assessment (MoCA) score ≤ 23 , 6) concurrent use of immediate release amantadine, and 7) are pregnant or plan to become pregnant.

c. Vulnerable Populations

None. Gender, ethnic origin, and minority status are neither inclusion nor exclusion criteria. Women and minorities will be included in this study. Children under the age of 18 will be excluded from this study. Subjects will not have mild to severe cognitive impairment.

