We will use an open-label trial design in which 12 participants will be given GOCOVRI™ provided by Adamas Pharmaceuticals, Inc. [name] (PI) will sign the medication order and prescribe the doses and the medication will be administered by the OHSU research pharmacy. A research coordinator will pick up the medication from the pharmacy prior to the baseline study visit to give to the subject with instructions about when to start taking the medication and how to increase dose over time. The drug will be administered orally once daily before bedtime. A forced four-week titration will be prescribed with the active treatment arm receiving 137mg/day (2 pills) during weeks 2 and 3 which will be increased to 274mg/day (4 pills; unless dyskinesia is relieved by the lower dose; then will stay at initial dose – increase will be based on clinical response to the lower dose) for weeks 4, 5 and 6 (see Figure 1). Participants will be contacted by a research assistant after the dosage is increased to ensure there are no issues, which if reported will be followed up by [name]. In addition, participants will be encouraged to call a study team member if they are having difficulty tolerating the medication at any point during the study. If the subjects experience side-effects at higher dose, then they will be asked to continue at the 137mg/day until after the second assessment, then tapered off in a single week. If patients wished to continue on GOCOVRI we will reach out to their provider and share their interest in wanting to remain on the medication. It will be explained to patients that they will only be guaranteed to receive GOCOVRI during the course of the study and future use will be at their and their provider's discretion with cost as determined by their individual insurance and pharmacy providers.

Data collection

Prior to the first study visit, participants will go to the OHSU outpatient Laboratory or a local laboratory who will assess renal function (unless this test has previously been completed with in the 30 days prior

to the first study visit). If renal impairment (estimated glomerular filtration rate (eGFR) < 50 ml/min/1.73 m²) is found, subjects will be excluded from the study, and the subjects will be informed of the results and the results will be sent to their primary care physician. Subjects will complete a blood pressure test for orthostatic hypotension (OH). If OH is found, the person will be excluded from the study.

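### For both aims, Section 8 gives its result as a list of significantly different metrics and plans no estimate or interval for the change; with at most 12 pairs, such a list says little about small to moderate effects

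*Combined protocol and SAP*

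**What the plan says.** Section 2 sets the aims as investigating the drug's effect on activity, gait and balance, and names the primary outcomes: "Primary outcome measures: Total number of steps and turns per day". Section 5.a fixes the size: "A total of 12 people with PD and LID will be recruited to the study". Section 6 (Drug dosage) confirms a single treated group: "We will use an open-label trial design in which 12 participants will be given GOCOVRI". Every comparison is therefore within person, with at most 12 pairs.

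Section 8 describes the Aim I analysis as "We will undertake analyses to determine which of our metrics are significantly different between Week 1" and Week 6, using "paired t-tests (if data appear normally distributed) or nonparametric Wilcoxon signed-rank test (data not normally distributed"). The Aim II analysis has the same form: "We will undertake analyses to determine which of our metrics are significantly different during the first hour of the day". After each, Section 8 says that significant changes are expected and that such a result would show the drug to be helping: with overall activity under Aim I, and with early-morning walking under Aim II.

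No section plans a mean or median change, a standardised effect or a confidence interval for Week 6 against Week 1. The mean and variability mentioned under Aim I define gait metrics such as stride length; they do not estimate a treatment change. The only other analysis in Section 8, relating metrics to dyskinesia, is exploratory and has no stated method or output.

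**The concern.** The aims ask how the drug affects activity and gait. The planned output says which metrics pass a test. In a 12-person study these are different questions, for two reasons.

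First, a small study can reach significance only when the observed change is large relative to its variability. If the true change is small or moderate, the metrics that pass are mostly those in which chance added to the effect.

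Second, a metric that fails the test may have changed by nothing or by a useful amount, and a list of significant metrics cannot show which. This applies in both directions. Section 3 motivates the study by more falls on active drug, so a non-significant worsening of gait or balance needs its size and precision stated as much as an improvement does.

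Section 8 also goes directly from significance in some metrics to a statement of benefit. The metric list is introduced by examples and so is open-ended, and nothing ties the conclusion to the size of change in the two primary outcomes.

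**Working it through.** **Inputs from the documents.** 12 participants (Section 5.a), one group measured before and after treatment (Section 6), and a paired t-test or Wilcoxon signed-rank test (Section 8).

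**Assumptions.** The documents give no alpha, power, effect size, SD of change or dropout rate, so the choice of 12 cannot be reproduced. The check uses a two-sided 5% level, normal paired differences, true mean changes d from 0.2 to 1.2 SD of the paired change, and 12, 10 or 9 completers.

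**Step 1: interval half-width.** In sample-SD units, the 95% half-width for the mean paired change is t(0.975, n−1)/√n. The same value is the smallest observed change that the t-test calls significant.

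- n = 12: 2.201/3.464 = 0.635
- n = 10: 2.262/3.162 = 0.715
- n = 9: 2.306/3 = 0.769

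**Step 2: power and average exaggeration.** Power comes from the noncentral t distribution with n−1 degrees of freedom and noncentrality d√n. Exaggeration is the average absolute mean change among significant results divided by the true change, from 400,000 simulated trials per scenario. For n = 12:

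| True change (SD) | Power | Average exaggeration if significant |
|---|---|---|
| 0.2 | 9.7% | 3.3-fold |
| 0.3 | 15.8% | 2.3-fold |
| 0.5 | 35.3% | 1.55-fold |
| 0.8 | 71.4% | 1.15-fold |
| 1.0 | 88.3% | 1.06-fold |
| 1.2 | 96.5% | 1.02-fold |

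With 10 completers, power at 0.3, 0.5, 0.8 and 1.0 SD is 13.6%, 29.3%, 61.6% and 80.3%, and exaggeration is 2.52-, 1.66-, 1.22- and 1.10-fold. A power of 80% needs a true change of 0.89 SD with 12 completers, 1.00 SD with 10 and 1.07 SD with 9.

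**Step 3: what a non-significant result leaves open.** With n = 12:

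- Observed 0.50 SD: 0.50 ± 0.635, or −0.14 to 1.14 SD
- Observed 0.30 SD: 0.30 ± 0.635, or −0.34 to 0.94 SD

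Both are non-significant, and both are compatible with no change and with a large one. A true change of 0.5 SD is missed with probability 1 − 0.353 = 0.647, about 65%.

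**Step 4: limits of these figures.** The 0.64 SD cut-off belongs to the t-test. The signed-rank test has no fixed cut-off on this scale: in simulation at a true 0.5 SD, about 4% of its significant results had an observed change below 0.635 sample SD. Overestimation is an average, not a rule for each result: among significant t-tests, the estimate falls below the truth 31% of the time at 0.8 SD, 43% at 1.0 SD and 48% at 1.2 SD.

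**The case against.** The strongest reply is that Section 8 is silent on estimates and does not exclude them. It names a test for each comparison. It does not say that only significant metrics will be reported, that sizes will be withheld, or that a non-significant metric counts as unchanged. A paired t-test is computed from the mean change and its standard error, so the estimate will be at hand, and nothing suggests that steps and turns per day would go unreported. A reader might infer a decision rule that suppresses effect sizes; the text does not support that reading.

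A reader might also infer that every significant change will be too large. That does not hold either. The bias depends on the true effect, which the documents do not give, and it is negligible at about 1 SD or more. Nor is 0.64 SD a threshold for every planned test.

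Finally, no data would be collected differently, and intervals could be added at the reporting stage.

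All of this stands as a limit on the claim. It does not remove the gap. Nothing commits the study to reporting estimates, and the one interpretive step that Section 8 does set out runs from significance to benefit without reference to size. If estimates are added only at reporting, the choice of which to show could itself follow significance.

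**Conclusion.** The point holds as a gap in the stated output. Section 8 specifies tests and a conclusion drawn from significance, but no estimate or interval for the change. If the true changes are small to moderate, a list of significant metrics would overstate them on average: 2.3-fold at 0.3 SD and 1.55-fold at 0.5 SD, falling to 1.15-fold at 0.8 SD and 1.06-fold at 1.0 SD. Whatever the true effect, a non-significant metric reported without an interval cannot be read as unchanged.

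These sizes rest on 12 complete pairs, normal differences and a two-sided 5% level; fewer completers make them worse. The planned tests are valid for their own purpose and the study stays usable without the change. In a 12-person single-group study, though, the size of the change and its precision are the main usable result, so the change should be made.

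**What to change.** In both Section 8 sentences, commit to reporting the paired Week 6 minus Week 1 change with its 95% confidence interval, in original units, for every listed metric whether or not it is significant. Put the primary outcomes, steps per day and turns per day, first. Use the mean with a t interval, or the Hodges-Lehmann estimate with the signed-rank interval where the Wilcoxon test is used.

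Add that non-significant metrics are described by their intervals and not as unchanged. Base the conclusion about activity on the size and interval of the two primary changes, not on which metrics reach significance.

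Intervals alone do not remove the exaggeration; reporting every listed metric is what prevents selection by significance. The planned tests and p-values can stay. Expressing changes as a percentage of Week 1 would be a matter of preference.

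The cost is a few lines of text and trivial programming, with no added participants, visits or procedures. The reported results will look less precise than a list of significant metrics would.
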